1.2 Secondary Aim

1.2.1 To further define the toxicities of the study arms in the treatment of translocation morphology RCC across all ages.

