2.2.3 Anti-angiogenic plus PD1 Inhibitor Combination Trials

Studies combining anti-angiogenic therapies and PD1 inhibitors in RCC have recently been performed. A trial of nivolumab plus sunitinib confirmed that combining each agent at full dose was tolerable (nivolumab up to 5 mg/kg IV q 3 weekly; sunitinib 50 mg PO daily 4 weeks on/2 weeks off) and demonstrated objective anti-tumor activity (41% ORR by 6 weeks); however, hepatotoxicity was noted. Similarly, combining nivolumab with pazopanib resulted in increased toxicity, notably hepatotoxicity. Specifically, in trial NCT01472081, patients with mRCC (≥ 1 prior systemic therapy) received nivolumab in combination with sunitinib (50 mg, 4 weeks on/2 weeks off; Arm S) or pazopanib (800 mg daily; Arm P), until progression/unacceptable toxicity. The starting dose of nivolumab was 2 mg/kg IV Q3W (N2), with planned escalation to 5 mg/kg IV Q3W (N5). Based on tolerability, the Arm S N5 cohort was expanded to treatment-naïve patients. Primary objectives were safety/tolerability and determination of maximum tolerated dose (MTD) for the combinations; the secondary objective was antitumor activity (ORR and duration of response [DOR]). Seven patients were assigned to each of Arms S N2 and N5. No dose-limiting toxicities (DLTs) were observed and a MTD was not reached, thus N5 was expanded with 19 additional patients (total n=33). Arm P enrolled 20 patients at N2; 4 DLTs (elevated ALT/AST [n=3], fatigue [n=1]) were observed, leading to closure of this arm. Grade 3–4 related AEs were observed in 24/33 patients (73%) in Arm S and 12/20 patients (60%) in Arm P. The most common related Grade 3–4 AEs included elevated ALT (18%), hypertension and hyponatremia (15% each) in Arm S and elevated ALT/AST (20% each) and fatigue (15%) in Arm P. Hepatotoxicities were manageable using treatment algorithms. Grade 3 pneumonitis occurred in 1 patient (Arm S, N5). Grade 3–4 related AEs led to therapy discontinuation in 8/33 patients

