9.0 STATISTICAL CONSIDERATIONS

9.1 Sample Size and Study Duration

As of Amendment 5A, which now allows crossover upon progression from the nivolumab arm to the nivolumab + axitinib arm, we expect enrollment of approximately 2 patients per month. This is derived from tRCC prevalence, access to treatment centers, and enrollment patterns to date, which should be aided by the crossover.

To reduce the overall sample size from the prior design, we have maintained the same overall study design but changed two design parameters: 1-sided alpha will be increased from 0.05 to 0.15, and the targeted hazard ratio will be reduced from $HR = 0.50$ to $HR = 0.40$. With these changes, 22 PFS events will be required to address the primary objective comparing Arms A and C at the time of final analysis (see [Section 9.2](#)). Allowing that approximately 25% of eligible and evaluable patients may not have experienced a PFS event by the time of the final analysis, the target accrual on this study is 28 patients. To account for an additional estimated 5% of patients who might be found to be ineligible for the study or inevaluable for the primary endpoint at the time of or following study enrollment (e.g., due to randomization to Arm B, no central path review performed, or having central path review confirming a diagnosis other than tRCC), the ceiling accrual will be set to 40 patients, including those patients already enrolled.

If the study accrues to the target accrual without interim stopping for futility, the additional time required to enroll up to this maximum once re-opening under Amendment 5A is estimated to be 14 months. As before, all eligible patients will be followed for 5 years after randomization, and the final analysis will be conducted once the target number of PFS events needed for the final analysis has been reached, or after 2 years of follow-up is obtained for the last patient enrolled, whichever occurs first.

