9.2 Study Design

With Amendment 5A, as before, eligible tRCC patients will be randomized to receive either axitinib and nivolumab (Arm A) or nivolumab alone (Arm C) in a 1:1 ratio. The enrolling institutions will assess the initial patient eligibility, including the type of RCC. Randomization will incorporate stratification for age (< 18 years vs. \geq 18 years), and prior systemic therapy for RCC (none, anti-VEGF based therapy, or systemic therapy other than anti-VEGF). Patients may receive their assigned therapy for up to 2 years or 26 cycles of therapy, whichever occurs first, as long as they do not experience either progressive disease as defined by the immune RECIST criteria (see [Section 10.2.5](#)) or unacceptable toxicities. The primary endpoint of this study is progression-free survival (PFS), defined as the time from randomization to the earliest of disease progression (according to RECIST adapted for immunotherapy) or death due to any cause (see [Sections 9.4](#) and [10.2](#)).

In planning the amended 2-arm design of this study, patient-level data on tRCC patients with metastatic disease who would have been eligible for AREN1721 were extracted from three separate cohorts: 7 patients from the cohort described by Ambalavanan and Geller, 15 patients from the cohort described by Malouf et al, and 3 patients from the COG study AREN03B2.^{34,24} PFS for the 3 cohorts was plotted together and found to be in agreement (log-rank test $p = 0.72$; Figure 1A). As such, these data were pooled into a single “historical” cohort used to select an appropriate parametric distribution for PFS in this disease setting from the proportional hazards family of models, from which determinants of power and sample size could be based. Upon superimposing the “best-fit” exponential, Weibull, and piecewise exponential models onto the Kaplan-Meier plot for PFS in the pooled historical cohort, it was determined that the piecewise exponential model offered a practically superior fit warranting the relative increase in model complexity (Figure 1B):

Figure 1A

[figure not shown]
[figure not shown]

Figure 1B

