A comprehensive simulation study was then performed, varying the following: the target sample size and maximum number of events required at the final analysis time point, the number and timing of interim analyses for futility, futility stopping strategies (conditional power under the alternative and current HR), and the true underlying hazard ratio (from $HR = 1.0$, the null hypothesis type I error scenario, to $HR = 0.40$, the target alternative hypothesis scenario). For all settings and strategies evaluated in simulations, accrual was assumed to be uniformly distributed as 24 patients per year (as reasoned above, acknowledging that slower than expected accrual will yield greater statistical power than reported here). PFS in the control arm was assumed to follow the piecewise exponential distribution shown in Figure 1B. With 100,000 replicates (simulated trials) used to assess each scenario, we arrived at the following trial design and set of operating characteristics.

The trial will enroll a target of 28 patients to observe 22 PFS events, which are required to achieve at least 80% power to detect a hazard ratio of $HR=0.40$ using a one-sided stratified log-rank test with $\alpha = 0.15$. If stratum-specific sample sizes allow, stratification of the test will include those factors used for stratification at the time of randomization (age and prior systemic therapy).

The trial will include one formal interim analyses for futility, conducted at 50% (11) of the required 22 PFS events. At this time, an observed hazard ratio greater than 1.00 (i.e., a

trend in the wrong direction) will result in early termination of the trial for futility. The simulated percentage change of early stopping for futility at the planned interim analysis (“early futility”), continuing to the final analysis but failing to reach statistical significance (“lack of efficacy”), and continuing to the final analysis and reaching statistical significance (“efficacy”) are tabled below for a range of true underlying hazard ratios. Also presented are the average simulated sample size (“Average N”) and average simulated time from reopening with Amendment 5A to final trial outcome (“Average Remaining Duration”) corresponding to each possible trial outcome. These numbers take into account the patients already enrolled, eligible, and anticipated to be evaluable for the primary endpoint.

True HR	Interim Analysis (50% Events)			Final Analysis (100% Events)			

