ORR: A logistic regression model for overall response, stratified by the stratification factors used at randomization (age and prior therapy) will be fit, including treatment arm as a key covariate. From this model, the odds ratio for treatment arm will be reported with a 70% confidence interval. The ORR observed within each treatment arm will also be reported.

OS: A stratified, one-sided log-rank test (using the stratification factors at randomization, age and prior therapy) will be performed to compare treatment arms with alpha = 0.15. Cox proportional hazards models will also be fit to evaluate the final hazard ratio between the treatment arms, with exploratory modeling taking into account the potential influence of other factors (e.g., baseline disease burden, upfront vs. delayed nephrectomy). From these models, the hazard ratio for treatment assignment will be reported with a 70% confidence interval (to align with the overall alpha level of the primary log-rank test).

AEs: All Grade 3 or higher non-hematologic toxicities and all Grade 4-5 adverse events occurring during protocol therapy or within 100 days of treatment discontinuation, including crossover for patients who receive crossover combination therapy, will be analyzed. The rates of these events will be reported separately by treatment arm (including crossover as a “3rd” arm for this purpose), and both by individual AE and class of AE (e.g., hematologic). Given that some AEs may be rare, Fisher Exact tests will be used to test for statistical significance among any apparent differences by treatment arm.

Exploratory Analyses

Exploratory Aim 1.3.1: To characterize tRCC clinical behavior across all age groups.
We will list and summarize the frequency of site(s) of disease at presentation (including extent of lymph node involvement), site(s) of relapse, surgical practices on protocol therapy, and radiotherapy practices on protocol therapy. We will also summarize the overall response rate (ORR) submitted by the enrolling institution.

Exploratory Aim 1.3.2: To evaluate type of antitumor immune response and stability of T cell activation before and after treatment with immunotherapy or antiangiogenic therapy.

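### Toxicity, the only secondary aim listed in 1.2, gets per-arm rates and Fisher tests with no stated alpha, but no between-arm difference or confidence interval; with about 14 patients per arm, a non-significant test says little.

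*Combined protocol and SAP*

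**What the plan says.** Section 1.2 contains a single aim: "To further define the toxicities of the study arms in the treatment of translocation morphology RCC across all ages". Section 9.3 lists Grade 3 non-hematologic and Grade 4 or higher AEs among the outcomes to be formally compared at the final analysis. Its AE paragraph first promises description: "The rates of these events will be reported separately by treatment arm", by individual AE and by class, with crossover treatment shown as a third group. The only between-arm method follows: "Fisher Exact tests will be used to test for statistical significance among any apparent differences by treatment arm". The paragraph gives no alpha, no sidedness, no risk difference or ratio, and no interval.

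The efficacy outcomes in 9.3 are handled differently. For ORR, "the odds ratio for treatment arm will be reported with a 70% confidence interval". PFS and OS each get a hazard ratio with a 70% interval, beside a one-sided log-rank test at 0.15.

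Section 9.5 adds a separate safety rule. Dose-limiting toxicities in the first four-week cycle are monitored in each arm against a limit of 3 in the first 10 patients and 30% thereafter. Excess in the combination arm suspends accrual.

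On size, "The trial will enroll a target of 28 patients to observe 22 PFS events", with randomization to axitinib plus nivolumab (Arm A) or "nivolumab alone (Arm C) in a 1:1 ratio". In 9.1, "the ceiling accrual will be set to 40 patients", which includes patients already enrolled. Section 10.2.2.1 makes all treated patients evaluable for toxicity.

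**The concern.** At this sample size, a significance test is a poor summary of a difference in harm. It can return a non-significant p-value when the true excess on the combination is large, and the p-value does not show how large an excess is still compatible with the data. Per-arm rates let a reader subtract one from the other, but they carry no uncertainty for that contrast. The boundary in 9.5 covers cycle 1 only, whereas treatment may run to 26 cycles and AEs are counted to 100 days after discontinuation. It also sets a limit within each arm and does not compare arms.

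The combination could thus be reported with a PFS hazard ratio and interval beside a toxicity comparison that has only a p-value. Because alpha and sidedness are not fixed, the same table could be called significant or not depending on a choice made after the data are seen.

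**Working it through.** The documents give no power or precision figure for AEs, so there is none to reproduce. The check asks how often the planned test would miss a given true difference.

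**Inputs**
- Arm size: 28/2 = 14 (9.2). As an upper bound under equal allocation, 40/2 = 20 (9.1). The true ceiling is lower, because the 40 includes any Arm B patients, whose number is not given.
- Alpha: not stated. Two conventions are shown: two-sided 0.05 (assumed), and one-sided 0.15 (the level 9.3 uses for PFS and OS).
- Rates: 19% is the Grade 3-4 rate on nivolumab alone in 2.2.2. For nivolumab with a different VEGFR inhibitor, 2.2.3 gives related Grade 3-4 rates of "24/33 patients (73%) in Arm S and 12/20 patients (60%) in Arm P". The pairs 20% vs 50% and 5% vs 25% are hypothetical, standing for AE classes and single AEs.

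**Formula.** With a and c patients affected in Arms A and C:

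Power = Σₐ Σ_c Bin(a; n, p_A) × Bin(c; n, p_C) × 1[Fisher p(a, c) ≤ α], summed over all tables. Miss rate = 1 − power.

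**Results (miss rates)**

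| True rates, C vs A | n = 14, two-sided 0.05 | n = 14, one-sided 0.15 | n = 20, two-sided 0.05 |
|---|---|---|---|
| 19% vs 73% | 27% | 4% | 10% |
| 19% vs 60% | 53% | 17% | 32% |
| 20% vs 50% | 74% | 38% | 59% |
| 5% vs 25% | 86% | 54% | 70% |

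At 14 per arm and two-sided 0.05, with 2/14 affected in Arm C, Arm A needs 8/14 to reach significance.

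**What an interval adds.** Take 7/14 in Arm A and 2/14 in Arm C. Fisher gives two-sided p = 0.10 and one-sided p = 0.052. The Wilson 95% limits are 0.268 to 0.732 for 7/14 and 0.040 to 0.399 for 2/14. The Newcombe interval for the difference d = 0.500 − 0.143 = 0.357 is:
- Lower: 0.357 − √[(0.500 − 0.268)² + (0.399 − 0.143)²] = 0.357 − 0.346 = 0.01
- Upper: 0.357 + √[(0.732 − 0.500)² + (0.143 − 0.040)²] = 0.357 + 0.254 = 0.61

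The result is +36 points (95% CI +1 to +61). The interval just excludes zero while Fisher does not reach 0.05, because the two methods differ and Fisher is conservative in small tables. With 7/14 vs 3/14, Fisher p = 0.24 and the difference is +29 points (95% CI −6 to +56; 70% CI +10 to +45). Both tables are non-significant at two-sided 0.05, yet both leave an excess above 40 points open.

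**More patients is not a realistic answer.** For 20% vs 50% with 80% power at two-sided 0.05, n per arm = [1.96√(2 × 0.35 × 0.65) + 0.842√(0.20 × 0.80 + 0.50 × 0.50)]² / 0.30² = 39, or 45 with continuity correction. That is 78 to 90 patients, against a ceiling of 40.

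**The case against.** A reader might infer that toxicity is judged only by Fisher tests, and that a non-significant result would dismiss a real safety penalty. The documents do not support that. Rates by arm, by AE and by class are reported. Section 9.5 monitors the combination arm without any p-value, and 12.2 gives the data and safety monitoring committee review of toxicity. The aim in 1.2.1 is descriptive, and nothing says that a non-significant test ends the matter.

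The miss rates can also be challenged. They depend on an alpha that the plan does not state. At one-sided 0.15 they run from 4% to 54%, and 7/14 vs 2/14 would count as significant. So it cannot be said without conditions that the test usually misses large excesses: even at two-sided 0.05, it detects 19% vs 73% in 73% of trials. The 14 per arm is the PFS target, and the toxicity arms may be larger. The 19%, 60% and 73% come from separate trials, the latter two with sunitinib and pazopanib rather than axitinib, and those trials' event definitions differ from the AE set in 9.3. Section 2.2.3 also describes axitinib with another PD-1 inhibitor as tolerable. Finally, a risk difference and interval can be computed from the rates already planned.

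All of this stands as a limit on the size of the point. It does not supply the missing estimate. That the interval is easy to compute is a reason to specify it, and that the miss rate for 20% vs 50% moves from 74% to 38% with an unstated choice is a reason to state it.

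**Conclusion.** The point holds as a gap in the planned analysis. It is not a finding that toxicity would be ignored. Among the outcomes that 9.3 sets out to compare formally, AEs alone have no between-arm estimate or interval, and toxicity is the only aim listed under 1.2. At 14 per arm the Fisher test misses between 27% and 86% of trials over the four rate pairs at an assumed two-sided 0.05, and between 4% and 54% at one-sided 0.15. At the 20-per-arm upper bound and two-sided 0.05, the range is 10% to 70%. These figures assume equal arms and independent binomial counts, and the rates are illustrative. On either convention, a non-significant result is weak evidence of no excess toxicity for anything short of a very large difference. The label is a cheap improvement.

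**What to change.** In the AE paragraph of 9.3, add the Arm A minus Arm C difference in the proportion of patients with (a) any Grade 3 or higher non-hematologic AE, (b) any Grade 4-5 AE, and (c) each main AE class, with a Newcombe or exact confidence interval at a stated level. Keep the Fisher p-values as descriptive, state their sidedness, and add a sentence that non-significance will not be read as absence of excess toxicity. Crossover patients are Arm C patients, so the third group is not independent of Arm C and should stay outside this contrast.

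The cost is a few lines of SAP text and one column in the AE tables, with no new data, patients or change to the primary test. The downside is that the intervals will be wide: the 95% interval in the 7/14 vs 2/14 example spans 60 points. No safety margin is proposed, because the documents give no basis for one.

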2.1.2 PD1/PD-L1 in tRCC and Nivolumab

Recent reports of possibly improved durable response rates using immune checkpoint inhibitor therapy for RCC^{26, 37, 38} as compared with historical data using cytokine therapy, coupled with the FDA approval of several such inhibitors for other cancers,^{26, 39} have propelled PD1/PD-L1 immune checkpoint inhibitor therapy to the forefront of many RCC-based clinical investigations. The PD-L1 ligand is not expressed in normal kidney but is expressed in many RCC specimens, including 25-30% of tRCC.^{26, 40, 41} Specifically, Chang et al reported 25% (9/36) tRCC express PD-L1 which was associated with advanced stage and poor prognosis. Interestingly, PD-L1 tumor expression is associated with a worse clinical outcome in general, and shorter overall survival (OS) in RCC patients treated with anti-VEGF RTKIs.⁴²

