We will summarize the levels of analytes and tumor expression before and after treatment and evaluate the changes due to treatment after logarithmic transformation using the paired t-test. Analytes include myeloid derived stem cells (MDSC): CD45, CD11b, CD33, CD14, CD15, HLA-DR, viability, stain 1; Tregs: viability, CD45, CD4, CD3, CD24, FoxP3; CD8 T cells (CD45, CD8, CD3); CD8 phenotype and activation and exhaustion (CD69, CD38, PD1, CD244, TIM3). Tumor expression of PDL-1, PD1, CD3, CD4 and CD8 will be assessed using TFE RCC samples from the study and scored for intensity (0 – 3).

Exploratory Aim 1.3.4: To characterize the pharmacokinetics of axitinib when given in combination with nivolumab in pediatric patients with tRCC.

The population PK analysis will include all treated patients enrolled beyond Amendment 5A who have at least 1 concentration above the below limit of quantitation (BLQ) in patients treated with axitinib. Pooled PK analysis with another study is to explore the effect of age and body size on axitinib CL/F and Vd/F and make predictions on the dosing of axitinib in pediatric patients in different age groups. Exposure-response relationships will also be explored. The results will be reported separately in a population modeling analysis report. For the purposes of PK analysis, patients who receive crossover therapy will be reported both as a separate cohort and pooled with patients receiving combination therapy up front.

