15.2.2 Immunotherapy Biomarkers in Tissue

Tissues will be used to assess PD-L1 expression and TIL composition/distribution before treatment using multicolor imaging.

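### Aim 1.3.2 prescribes a log transform and paired t-test for tumour scores on a 0–3 scale, so the test is undefined for any pair containing a 0 (minor)

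*Combined protocol and SAP*

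**What the plan says.** Section 9.3, under Exploratory Aim 1.3.2, opens with a sentence covering two kinds of variable: "We will summarize the levels of analytes and tumor expression before and after treatment". The same sentence gives a single method for both, which is to "evaluate the changes due to treatment after logarithmic transformation using the paired t-test".

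The paragraph then lists the flow-cytometry analytes and turns to the tissue markers. Tumour expression of PD-L1, PD1, CD3, CD4 and CD8 "will be assessed using TFE RCC samples from the study and scored for intensity (0 – 3"). That is a four-level ordinal scale that includes 0.

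Neither section 9.3 nor the tissue assay sections (15.2.2 to 15.2.2.6) gives an offset, a rule for zeros or a separate method for the ordinal scores. No sample size, alpha or power is stated for this aim.

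Two other places bear on the size of the problem:

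- **Frequency of expression.** Section 2.1.2 says that PD-L1 "is expressed in many RCC specimens, including 25-30% of tRCC", and cites one series in which "25% (9/36) tRCC express PD-L1 which was associated with advanced stage and poor prognosis".
- **Availability of pairs.** Section 15.2.2 describes the tissue work as a baseline assessment: "Tissues will be used to assess PD-L1 expression and TIL composition/distribution before treatment using multicolor imaging". Section 15.2.2.1 limits on-therapy tissue to samples taken for a clinical reason, from consenting patients.

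**The concern.** A log transform followed by a paired t-test needs strictly positive values measured on a scale where ratios mean something. A 0–3 intensity score meets neither condition. When a score is 0 the log is undefined, and the analyst must choose a workaround that the plan does not name. Even without zeros the log spaces the categories oddly: the step from 1 to 2 becomes ln 2 = 0.69 and the step from 2 to 3 becomes ln 1.5 = 0.41, with no biological reason for the difference.

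What is at stake is the before/after description of tumour immune markers in a rare cancer whose tissue is hard to replace. With few pairs, a workaround chosen after seeing the data could decide what is reported.

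**Working it through.** **Inputs from the documents.** PD-L1 expression in tRCC: 25–30% (section 2.1.2). Target accrual 28, ceiling 40 (section 9.1). Tissue scale 0, 1, 2, 3 (section 9.3).

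**Inputs assumed.** Non-expressing means intensity 0. The number of tissue pairs is not stated; 5 and 10 are shown. Expression of 50% and 60% is shown as a range, because section 2.1.2 links expression with advanced stage.

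**1. The protocol's own figure.** 9/36 = 0.25, which matches the cited 25%.

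**2. Expected PD-L1 zeros at baseline.** Expected zeros = N × (1 − p).

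| N | p = 0.25 | p = 0.30 | p = 0.50 | p = 0.60 |
|---|---|---|---|---|
| 28 | 21.0 | 19.6 | 14.0 | 11.2 |
| 40 | 30.0 | 28.0 | 20.0 | 16.0 |

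The exact binomial probability that more than half the scores are 0 at N = 28 is 0.996 (p = 0.25), 0.979 (0.30), 0.43 (0.50) and 0.10 (0.60). A majority of zeros therefore depends on the assumed rate.

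**3. Chance that at least one pair has a baseline zero.** 1 − p^m for m pairs.

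| Pairs | p = 0.25 | p = 0.30 | p = 0.50 | p = 0.60 |
|---|---|---|---|---|
| 5 | 0.999 | 0.998 | 0.97 | 0.92 |
| 10 | >0.999 | >0.999 | 0.999 | 0.99 |

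Meeting at least one zero is close to certain across the range. Pairs expected to have a non-zero PD-L1 baseline (m × p) are 1.25–1.5 of 5 or 2.5–3 of 10 at p = 0.25–0.30, and 2.5 of 5 or 5 of 10 at p = 0.50.

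**4. Can the stated test be run?** Take eight made-up pairs: before 0, 0, 0, 1, 0, 2, 0, 0; after 1, 0, 2, 2, 0, 1, 1, 0. The logs contain minus infinity and the paired t-test returns no value. Removing pairs that contain a 0 leaves 2 of 8; the three changes from 0 to positive are among those removed.

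**5. Does an offset settle it?** With log(x + c), the step from 0 to 1 is ln((1 + c)/c): 4.62 at c = 0.01 but 0.69 at c = 1. The step from 2 to 3 is 0.40 and 0.29 respectively. In the eight pairs above this matters little: p = 0.083, 0.090, 0.107 and 0.120 for c = 0.01, 0.1, 0.5 and 1.

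It can matter a great deal. Take ten made-up pairs: four rise from 1 to 2, three rise from 2 to 3, one falls from 1 to 0 and two stay at 0.

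| c | Mean log change | p |
|---|---|---|
| 0.01 | −0.065 | 0.90 |
| 0.1 | 0.136 | 0.65 |
| 0.5 | 0.195 | 0.24 |
| 1 | 0.179 | 0.13 |

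Seven of the eight changes are rises, yet the smallest offset gives a negative mean.

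**6. An ordinal paired test on the same data.** The exact two-sided signed-rank p is 10/32 = 0.31 for the eight pairs (five changed). For the ten pairs all eight changes are one step, so the signed-rank and sign tests agree: 2 × (1 + 8)/2^8 = 0.070. Both can be computed without any arbitrary constant.

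**The case against.** The strongest reply is that this is loose drafting. The log transform and paired t-test suit the blood analytes, which have scheduled repeat draws (section 15.2.1.1), while the tissue work is described as pre-treatment and later tissue is incidental. The failure is also visible when the analysis is run, so it would not mislead silently. Much of this stands, and it limits the importance of the point. It does not remove it: the sentence names tumour expression, and if the test was never meant for tissue, the 0–3 scores have no specified test. The same edit is needed either way.

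Three stronger readings are tempting, and the documents do not support them.

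- **That most tumours will score 0 for PD-L1 by the protocol's own figure.** Section 2.1.2 gives no positivity cut-off and does not equate non-expression with intensity 0. It ties expression to advanced stage, and this trial enrols only unresectable or metastatic disease, so positives may exceed 25–30%. The figure covers one of five markers.
- **That all changes from 0 to positive are necessarily lost.** That follows only if zero pairs are dropped. An offset keeps them, at the price shown above, and how much the offset matters depends on the data.
- **That the trial's conclusions are at risk.** The aim is exploratory, on optional specimens, with no stated sample size or error rate.

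It is also fair to say that an ordinal test gains little inferentially. The usual signed-rank and sign tests ignore unchanged pairs, including those at 0 both times. With five changed pairs the smallest two-sided exact p is 2/32 = 0.0625. The cross-table is the more useful part of the remedy.

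**Conclusion.** The point holds in a narrow form, and it is minor. As written, the method cannot be computed for any tissue pair containing a 0, and the plan does not say what to do then. This follows from the wording of section 9.3 and needs no assumption about frequency.

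How often it bites is uncertain. For PD-L1, up to about 70–75% of baseline scores could be 0 if non-expressing means intensity 0, and fewer if expression is higher in advanced disease. For PD1, CD3, CD4 and CD8 the documents give no rates. The number of tissue pairs is unstated and probably small. The PFS, OS, ORR and safety analyses are untouched.

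**What to change.** Amend the Aim 1.3.2 paragraph in section 9.3 as follows:

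1. Restrict the log transform and paired t-test to the continuous flow-cytometry analytes, and state in advance how a zero is handled.
2. For each tissue marker scored 0–3, report a before/after cross-table and the number of pairs. Test the untransformed paired changes with an exact Wilcoxon signed-rank or sign test, choosing one now. Note that tied pairs do not contribute and that the test has little power with few pairs.

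The cost is about two sentences. No additional samples, visits or data are required.
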